6 RESEARCH METHODS

6.1 Study Design

This will be a non-interventional multi-center cohort study of patients initiating inebilizumab conducted with secondary data sources in France, Germany, Italy, the Netherlands, and Spain. The study will be based on a cohort-event monitoring design to capture both drug utilization and selected safety outcomes in patients initiating inebilizumab. The proposed study design allows for an efficient initial descriptive evaluation of AESI.

The **study period** in individual countries will start on different dates, depending on the launching time of the drug (the earliest in the second quarter of 2022) (Table 1). The end of the study period will be also country-specific (the latest in December 2027) and will depend on the dates of data availability in individual data sources (different lag times and data release dates).

Table 1 Study periods, by country

	France	Germany	Italy	Netherlands	Spain
	SNDS/ NOMADMUS	GKV	RISM	PHARMO	SIDIAP
Launch date (quarter, year)	Q2, 2022	Q3, 2022	Q2 2023	Q3, 2023	Q2, 2023
Start of study period	May 2022	Aug 2022	May 2023	Aug 2023	May 2023
End of study period	Dec 2026	Dec 2026	Dec 2027	Dec 2026	Sep 2027
Study period duration (months)	57	54	56	41	53

Q2, 2nd quartile; Q3, 3rd quartile

The study population will be constituted by a cohort of adult female and male patients diagnosed with NMOSD with entry trigger by inebilizumab initiation.

[figure not shown]
The **index date** (Day 0) will be defined as the date of first treatment (date of administration/prescription/dispensation, depending on data available in selected data sources) (Figure 1). Patients initiating the treatment will be identified throughout the study period. After the index date, enrolled patients will be followed for 12 months or censored at end of study period or loss of follow-up (death, disenrollment/de-registering) whichever occurs first.

A **baseline period**, including any time from when data are available up to the index date, will be used to establish comorbidities and NMOSD-related clinical characteristics, whereas a short period of 6 months prior to or at index date will be used to determine previous immunosuppressive therapies.

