NMOSD disease burden and clinical characteristics up to the index date will include the presence of each of the diagnoses part of the NMOSD core symptom, disease duration, AQP4 and MOG seropositivity, NMOSD-associated conditions, history of relapses, and previous acute and maintenance therapies.

Disease duration will be estimated as the difference between the index date and the first NMOSD diagnosis date.

Where available, laboratory results most recent to the index date will be used to classify patients according to the presence of autoantibodies against AQP4 and MOG. Patients will be classified as positive, negative or unknown serology. As it is recommended to repeat AQP4-antibody testing if the result is non-conclusive or negative, the presence of at least one positive result will be sufficient to classify the patient as positive. Thus, data on serology during follow-up will be also analysed to present the most updated serology status of the patients.

Information on spinal cord and brain Magnetic Resonance Imaging (MRI) scans performed in the previous year will be extracted whenever available in the data sources. Patients will be defined as having had performed spinal MRI only, brain MRI only, spinal and brain MRI or no MRI scan in the previous year.

NMOSD as an autoimmune disease has been reported to coincide with other disorders including systemic autoimmune diseases, organ-specific autoimmune diseases, and other diseases with possible immunologic pathogenesis (13). The association of clinical or even subclinical autoimmunity is a supportive feature for the diagnosis of the disease (14).

NMOSD-associated conditions listed below will be identified by the respective ICD-9/ICD-10 codes (**Error! Reference source not found.** in Annex 3):

- Hypothyroidism
- Pernicious anemia
- Ulcerative colitis
- Myasthenia gravis
- Idiopathic thrombocytopenic purpura
- Hemiplegia/paraplegia
- Bladder dysfunction
- Neuropathic pain
- Antiphospholipid syndrome
- Sarcoidosis
- Scleroderma
- Sjogren’s syndrome
- Systemic lupus erythematosus
- Dorsalgia
- Disorders of lipoprotein metabolism and other lipidemias
- Other acute disseminated demyelination
- Disorders of refraction and accommodation
- Visual disturbances
- Disturbances of skin sensation
- Somatoform disorders
- Other dorsopathies, not elsewhere classified

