6.4.1 France

The French National Health Data System (Système National des Données de Santé [SNDS])

SNDS is the largest and most comprehensive healthcare dataset available in Europe with a 10-year longitudinal follow-up for more than 65 million individuals (including 50 million adults), and is highly representative of the French residents, covering 99% of the total population (15). Individuals enter the data source once born within or immigrating to the specific geographical area, and exit the data source either at date of death, emigration, or ending their insurance.

SNDS contains anonymized administrative and healthcare claims data from the French national health care insurance system databases including main health care claims database, ie., French National health insurance information system (*Système national d'information interrégimes de l'Assurance maladie* [SNIIRAM]), hospital discharge summaries (*Programme de Médicalisation des Systèmes d'Information* [PMSI]), and national death registry (Centre d'épidémiologie sur les causes médicales de Décès) (16).

SNDS contains information on beneficiaries age, sex, region of residence, death date, complementary universal health coverage status, and all out-patient healthcare drugs including all reimbursed prescription drugs identified by their ATC code, the date of delivery, quantity, and brand name. Medical procedures performed on an out-patient basis or in a healthcare institution are identified by the common classification of medical procedures (*classification commune des actes médicaux*), laboratory procedures are identified by the clinical pathology test nomenclature (*nomenclature des actes de biologie médicale*), and paramedical or medical visits are identified by the general nomenclature of professional procedures (*nomenclature générale des actes professionnel*).

The French National Health Insurance Information System, SNIIRAM

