6.4.2 Germany

German Government Health Insurance (*Gesetzliche Krankenversicherung* [GKV]) claims from approximately 8-10 different statutory health insurance providers (SHIs) are collected by Team Gesundheit. This is an established research institute which has been working for more than 1000 health insurance companies, companies and ministries since 1997. With branches in Essen, Hamburg, Bielefeld, Berlin, Frankfurt and Munich they are active in German health management nationwide. Since an SHI is a requirement for individuals with a permanent place of residence in Germany, even for short-term stays, the general population coverage in the SHI is considered nationwide. The SHIs also allow insurance coverage for children and spouses within a family insurance policy. The population size available through Team Gesundheit is approximately 5 million individuals which represents an estimated 6.9% of the SHI-insured population in Germany. Available data history through collaboration with Team Gesundheit reaches back to January 2008. Since 2012 all individuals in Germany have lifelong specific ID and SHI numbers which would not change throughout lifetime.

The database contains information from primary care, in- and out-patient hospital care as well as sick leaves. Relevant measures are available in the German database allowing demographic characteristics, treatments, healthcare utilization and clinical outcomes to be assessed, for example:

- registration data including age, gender;
- out-patient care data including ICD-10 diagnoses (not granular and per quarter), physician specialty
- inpatient care claim including ICD-10 diagnoses (up to 3 principal and 30 secondary diagnoses per stay), billed diagnosis-related group (German classification), up to 30 OPS-Codes per stay, duration of hospitalizations, and medical department; drug prescription data including ATC codes of prescribed medications

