6.4.3 Spain

The Information System for Research in Primary Care (*Sistema d'Informació per al Desenvolupament de la Investigació en Atenció Primària* [SIDIAP]), IDIAP Jordi Gol (Spain) is a primary care records database that covers approximately 7 million people, equivalent to an 80% of the population of Catalonia, North-East Spain. SIDIAP is collected from EHR records of patients receiving primary care delivered through Primary Care Teams (PCT), consisting of general practitioners, nurses and non-clinical staff. The Catalan Health Institute manages 286 out of 370 such PCT with a coverage of 5.6 million patients, out of 7.8 million people in the Catalan population (74%). The database started to collect data in 2006. The mean follow-up is 10 years. The observation period for a patient can be the start of the database (2006), or when a person is assigned to a Catalan Health Institute primary care center. Date of exit can be when a person is transferred-out to a primary care center that does not pertain to the Catalan Health Institute, or date of death, or date of end of follow-up in the database. Drug information is available from prescriptions and from dispensing records in pharmacies. Studies using SIDIAP data require previous approval by both a Scientific and an Ethics Committee (20). For a subset of patients included in the SIDIAP database, linkage to hospital data is available as obtained from the Catalan Institute of Health hospitals (21) and will be further explored in the feasibility assessment. Healthcare is universal and taxpayer funded in the region, and primary care physicians are gatekeepers for all care and responsible for repeat prescriptions. SIDIAP-Hospitalization Linked Data has contributed to studies involving patients with MS (21).

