6.4.4 Italy

The Italian Multiple Sclerosis & Related Disorders Register (*Registro Italiano Sclerosi Multipla e Patologie Correlate* [RISM]) was officially established in 2015. As of February 2023, the register was actively covering 133 MS centers, corresponding to a total of 80,353 patients, of which 273 are diagnosed with NMOSD. Since July 2022, the

register comprises a module for the collection of information on NMOSD, and has projects dedicated to NMOSD patients (22). Nonetheless, data on NMOSD patients were collected previous to 2022, without a specific module implemented. The data are collected from participating centers through a web-based system developed for the study, available at the IMS&RD website. Data are collected from accrual to exit of database, which may occur at date of death, when patient moves to a center outside of the covered network or withdraws their consent to participate. The data are centrally monitored to ensure quality of data, completeness, accuracy, and consistence (23). Requests to access the data are evaluated by the Scientific Committee, composed by clinicians, methodologists, representatives of MS centers, and of the Italian Neurological Society (23).

To ensure the collection of sufficient data for the clinical characterization of the single patient mandatory variables collected by the register include patient identification, demographics, vital status, disease onset date, diagnosis date, relapses, treatments and severe adverse events. This minimum dataset may be completed with an extension to optional information on family history, comorbidities, laboratory tests and MRI. Furthermore, the register has data on patient's unique personal identifier, to avoid inclusion of the same patient by more than 1 center. Diagnosis information is available and captured with ICD-9-CM coding system.

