The Hospital Database comprises datasets containing information on hospital admissions, ambulatory consultations, and high budget impact medication. The Hospital Database is collected and maintained by the Dutch Hospital Data Foundation and comprises records from nearly all hospitals in the Netherlands. With permission from each hospital the data are linked for research purposes with the PHARMO Database Network via the TTP. For more information, please see www.dhd.nl. Permission on a project basis is needed to obtain these data.

Hospital Admissions

This dataset comprises hospital admissions lasting more than 24 hours and admissions for less than 24 hours for which a bed is required (i.e., inpatient records). The records include information on hospital admission and discharge dates, discharge diagnoses and procedures. Diagnoses are coded according to the WHO ICD and procedures are coded according to the Dutch Hospital Data Foundation registration system for procedures (27)

which links to the Dutch Healthcare Authority (*Nederlandse Zorgautoriteit*, NZa) declaration codes (28) and the Dutch Classification of Procedures (29). Currently, PHARMO has access to data from 1998 onwards and of over 80% of the hospitals.

Ambulatory Consultations

This dataset comprises all ambulatory consultations (i.e., out-patient records). The records include information on each contact, including date, diagnoses and procedures. Diagnoses are coded according to the WHO ICD and procedures are coded according to the Dutch Hospital Data Foundation registration system for procedures which link to the Dutch Healthcare Authority declaration codes and the Dutch Classification of Procedures. Currently, PHARMO has access to data from 2016 onwards and of over 50% of the hospitals.

High Budget Impact Medication

In the Netherlands high budget impact medication is dispensed through hospitals. The dataset comprises all dispensed high budget impact medication. This data is available for all patients identified in the ambulatory consultation dataset. The records include information on date of dispensing, type of medication, number of units, indication of use and prescriber. Drug dispensing are coded according to the Dutch Z-index code (30). Currently, PHARMO has access to data from 2017 onwards and of over 50% of the hospitals.

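### Disease duration is only a lower bound for patients diagnosed before their claims or EHR data begin, and the cap differs by source, so means and upper percentiles are not comparable (minor, cheap to improve)

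*Protocol*

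**What the plan says.** Section 6.3.2 defines the variable in one sentence for all sources: "Disease duration will be estimated as the difference between the index date and the first NMOSD diagnosis date". Under section 6.1, the baseline period for NMOSD characteristics is open-ended, "including any time from when data are available up to the index date".

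Section 6.4 describes histories of very different length:

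- **SNDS (France):** "10-year longitudinal follow-up for more than 65 million individuals".
- **GKV (Germany):** "Available data history through collaboration with Team Gesundheit reaches back to January 2008".
- **SIDIAP (Spain):** "The database started to collect data in 2006. The mean follow-up is 10 years".
- **PHARMO (Netherlands):** for ambulatory consultations, "Currently, PHARMO has access to data from 2016 onwards and of over 50% of the hospitals"; hospital admissions go back to 1998.
- **RISM (Italy):** the mandatory fields include "disease onset date, diagnosis date, relapses, treatments and severe adverse events".

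Table 1 pairs SNDS with the NOMADMUS registry for France. Section 6.4.1 does not say whether NOMADMUS holds a diagnosis date.

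Section 6.7.1 asks for mean, median, quartiles and the 5th and 95th percentiles of continuous variables, by country or data source. The comparability limitation in section 6.9 names dose, biomarker results and MRI, but not disease duration.

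**The concern.** Where no clinical diagnosis date is recorded, the first NMOSD diagnosis date can only be the first code found in the history the source makes available. A patient diagnosed before that history starts cannot be given more years than the history contains. The formula then returns the length of the look-back, or less, and nothing marks the value as incomplete. RISM returns the real interval under the same formula.

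Disease duration is one of the characteristics named under objective 1. A reader who compares countries could take a difference in data history for a difference in how early in the disease inebilizumab is started. Other historical variables in section 6.3.2 are less exposed: relapses are counted over 1 and 2 years, MRI over one year, and prior therapies over 6 months. Disease duration is a length of time read from a look-back with no fixed limit, and it has no source-specific rule.

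**Working it through.** The protocol states no figure for disease duration, so there is none to reproduce.

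**Step 1: longest observable duration.** This is the index date (Table 1, first and last possible) minus the start of data (section 6.4). January is assumed where only a year is given. The earliest launch is "the earliest in the second quarter of 2022".

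| Source | Data start | Index range | Longest observable (years) |
|---|---|---|---|
| SNDS | 10 years as stated | May 2022 to Dec 2026 | about 10 |
| GKV | Jan 2008 | Aug 2022 to Dec 2026 | 14.6 to 18.9 |
| SIDIAP | 2006 | May 2023 to Sep 2027 | 17.3 to 21.7 from database start; mean personal follow-up 10 |
| PHARMO ambulatory | 2016 | Aug 2023 to Dec 2026 | 7.6 to 10.9 |
| PHARMO admissions | 1998 | Aug 2023 to Dec 2026 | 25.6 to 28.9 |
| RISM | diagnosis date recorded | May 2023 to Dec 2027 | no cap from data start |

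Example: GKV, January 2008 to August 2022, is 14 years 7 months = 14.6 years. If SNDS could be used back to the creation of SNIIRAM in 2003, its range would be 19.3 to 23.9 years, but the protocol describes 10.

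**Step 2: effect on the mean.** Let D be true time since diagnosis and L the look-back. The observed value is at most min(D, L). Assume D is exponential with mean μ = 4, 7 or 10 years and one L for all patients. Then E[min(D, L)] = μ(1 − e^(−L/μ)), and the relative shortfall is e^(−L/μ), which is also the share of patients capped.

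| L (years) | μ = 4 | μ = 7 | μ = 10 |
|---|---|---|---|
| 7.6 | 15% | 34% | 47% |
| 10 | 8% | 24% | 37% |
| 14.6 | 3% | 12% | 23% |
| 17.3 | 1% | 8% | 18% |

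For μ = 7 and L = 10, the observed mean is at most 7 × (1 − 0.240) = 5.32 years.

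**Step 3: effect on percentiles under the same assumption.**

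- Median, μ ln 2: 2.8, 4.9 and 6.9 years. All lie below 7.6, so the cap alone does not move the median.
- Third quartile, μ ln 4: 5.5, 9.7 and 13.9 years. At L = 10 only the last is cut.
- 95th percentile, μ ln 20: 12.0, 21.0 and 30.0 years. All three exceed 10, so a 10-year source reports at most 10.

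**Step 4: a different shape.** For D uniform on 0 to T with L < T, the shortfall in the mean is (1 − L/T)². For T = 15, 20 and 25:

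- L = 10: (5/15)² = 11%, (10/20)² = 25%, (15/25)² = 36%.
- L = 14.6: (0.4/15)² = 0.1%, (5.4/20)² = 7%, (10.4/25)² = 17%.

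With T = 25 the true median of 12.5 years would be cut at L = 10. The finding that the median is safe therefore depends on the assumed distribution.

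These calculations place a capped patient's first code exactly at the start of the data. A later first code makes the shortfall larger.

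**The case against.** The strongest reply is that this belongs to the SAP. Section 6.3.2 leaves detailed operational definitions to it and allows variables to be refined by database, and section 6.7.1 assigns full variable definitions to it. Nothing forbids using a recorded diagnosis date or flagging a short look-back. That stands for the details. But the protocol already fixes the formula for every source, and the limitations in section 6.9 are the protocol's own text. Section 6.9 does warn that administrative data may be incomplete and that registries may help. That is relevant but generic.

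A reader might infer that all claims-based countries will appear to treat earlier than Italy purely because of data history. The documents do not support that, for four reasons:

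- The long histories of GKV and PHARMO admissions leave little or no shortfall in several scenarios. PHARMO sources are linked at patient level, so the 2016 start binds only patients not coded in an earlier linked source.
- France also has NOMADMUS, which may hold diagnosis dates.
- Table 2 accepts optic neuritis and myelitis codes as defining NMOSD. If such a code starts the clock, duration in claims data could come out longer than a registry's diagnosis-based value.
- Results are reported by data source, and meta-analysis is optional and confined to specified outcomes. The protocol therefore does not commit to a pooled mean duration.

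It is also fair that the size rests on assumed distributions and that the median is prescribed alongside the mean.

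**Conclusion.** The point holds as a minor one. The stated rule gives a lower bound for patients diagnosed before their data begin, in sources without a recorded diagnosis date. The bound differs by source, and section 6.9 does not say so. Means and upper percentiles are understated by differing amounts and should not be compared across sources as they stand. Medians may be little affected.

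On assumed exponential durations with mean 4 to 10 years, the shortfall in the mean is about 8 to 37% at a 10-year look-back and 3 to 23% at 14.6 years. The protocol offers no duration distribution to narrow this. The subgroup over 65 is probably affected most, since section 4.1 puts mean age at onset near 40.

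Disease duration does not enter the treatment-pattern or AESI estimates, and the study tests no hypothesis. The consequence is limited to how one baseline characteristic is read across countries.

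**What to change.** - In RISM, use the recorded diagnosis date; do the same in NOMADMUS if it holds one.
- In the other sources, label the variable 'time since first recorded NMOSD diagnosis' and report the look-back available per patient.
- Flag as 'at least x years' any patient whose first code falls at the start of the observable history. Use an open top category set by the look-back each source supports, rather than one arbitrary cut-off for all.
- State whether optic neuritis or myelitis codes from Table 2 start the clock, or only the neuromyelitis optica code.
- Add one sentence on left truncation of disease duration to section 6.9.

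No new data are needed. The cost is some extra derivation and table-shell work, and less use of means in some sources.

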History of relapses will be ascertained depending on available data in the data sources (e.g., using documented relapse episodes as defined by individual disease-specific registries or considering the previous use of acute treatments such as intravenous corticosteroids, intravenous immunoglobulin or plasmapheresis therapy, or hospital admission with selected principal diagnoses) and will be defined in detail in SAP. Patients will be characterized according to the number of relapses in the previous 1 and 2 years (none, one, two or more).

Baseline use of **acute treatments** will include intravenous corticosteroids, intravenous immunoglobulin or plasmapheresis therapy in a 6-month period prior to the index date ([Table 7](#) NMOSD-Associated Conditions)

NMOSD-associated Conditions	Diagnosis ICD-9-CM Codes*	Diagnosis ICD-10-CM Codes*
Hypothyroidism	244.x	E89.0, E03.2, E03.8, E03.9
Pernicious anemia	281.0, 281.1	D51.x
Ulcerative colitis	556.x [excl. 556.2 and 556.3]	K51.xx [excl. K51.2x and K51.3x]
Myasthenia gravis	358.0x	G70.0x
Idiopathic thrombocytopenic purpura	446.6	M31.1
Hemiplegia/paraplegia	334.1, 342.x, 343.x, 344.0x-344.6x, 344.9	G11.4, G81.xx, G80.x, G83.0, G83.1x, G83.2x, G83.3x, G83.4, G83.9, G82.xx

NMOSD-associated Conditions	Diagnosis ICD-9-CM Codes*	Diagnosis ICD-10-CM Codes*
Bladder dysfunction	788.30, 788.31, 788.33, 788.34, 788.36, 788.37, 788.39-788.43, 596.xx	N30.xx, N31.x, N32.xx, N33
Neuropathic pain	353.x, 354.x, 355.x, 356.x, 357.x, 250.6, 729.2, 782	E08.40-E08.42, E09.40, E09.42, E10.40-E10.42, E11.40-E11.42, E13.40-E13.42, G50.0, G50.1, G54.x, G55.x, G56.x, G57.x, G58.x, G60.x, G61.x, G62.x, G63, G64, G65.x, G90.5x, M05.5x, M79.2, M54.1, R20
Antiphospholipid syndrome	289.81	D68.61
Sarcoidosis	135	D86.xx
Scleroderma	357.4, 359.6, 517.2, 701.0, 710.1	M34.xx, L90.0, L94.0, L94.1, L94.3
Sjogren's syndrome	710.2	M35.0x
Systemic lupus erythematosus	710	M32.xx
Dorsalgia	724.5	M54
Disorders of lipoprotein metabolism and other lipidemias	272.0, 272.1, 272.2, 272.3, 272.4, 272.5, 272.9	E78
Other acute disseminated demyelination	341.9	G36.9
Disorders of refraction and accommodation	367	H52
Visual disturbances	368	H53
Disturbances of skin sensation	782	R20
Somatoform disorders	300.81	F45
Other dorsopathies, not elsewhere classified	723.2, 723.3, 723.8, 723.9	M53

Abbreviations: ICD-9/ICD-10, 9th/10th Revision of International Classification of Diseases; CM, Clinical Modification; NMOSD, Neuromyelitis optica spectrum disorder

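### Relapses are counted over fixed 1- and 2-year windows with no requirement that those years were observed, so patients with short histories can be recorded as relapse-free

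*Protocol*

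**What the plan says.** Section 6.3.2 (Characterization Variables) treats relapse history in two steps.

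- **Ascertainment** depends on the source. Registries may supply it "using documented relapse episodes as defined by individual disease-specific registries". Otherwise it may be inferred by "considering the previous use of acute treatments such as intravenous corticosteroids, intravenous immunoglobulin or plasmapheresis therapy, or hospital admission with selected principal diagnoses". Both are given as examples, and the definition "and will be defined in detail in SAP".
- **Reporting** is then fixed without any deferral: "Patients will be characterized according to the number of relapses in the previous 1 and 2 years (none, one, two or more").

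Other sections determine who is classified and on how much history:

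- Section 6.1 defines the baseline period as "including any time from when data are available up to the index date, will be used to establish comorbidities and NMOSD-related clinical characteristics". No minimum length is given.
- Section 6.2.1 looks back only to confirm that no inebilizumab was given in the 6 months before index. It does not ask for continuous enrolment or observation. Section 6.2.2 applies no exclusions.
- Section 6.7.2.1 describes all new users under objective 1.
- Section 6.3.2 gives antibody serology an unknown category; relapse history has none.
- Section 6.7.1 says counts and percentages of missing values will be reported for categorical variables.
- Section 6.4.4 says of the Italian register (RISM): "Data are collected from accrual to exit of database".

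**The concern.** A count over the previous two years means what it says only if those two years were seen. Where relapses are inferred from treatment or admission records, a period outside observation produces no records, and no records looks the same as no relapses. A patient who entered the source six months before the first infusion has 18 of the 24 months unseen, yet the three planned categories offer nowhere to put that patient except by the events that happen to be visible.

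Relapse history is one of the NMOSD characteristics named for objective 1. It helps show whether inebilizumab is started in patients with recent, repeated attacks or in patients whose disease has been quiet. If short histories are read as quiet disease, the reported distribution mixes disease activity with length of data history. Results are to be presented by data source (6.7.1), so differences in look-back between sources could also be read as differences in the patients treated.

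**Working it through.** **Plan's own figure.** The protocol gives no expected relapse rate, no expected distribution of relapse history and no expected length of individual look-back. There is nothing to reproduce, and any size is illustrative.

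**Does the text lead to the misclassification?**

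1. The windows are fixed at 1 and 2 years (6.3.2).
2. The data available to fill them run from each patient's entry into the source, whenever that was (6.1).
3. No eligibility rule removes patients whose entry falls inside the window (6.2.1, 6.2.2), and objective 1 describes them all (6.7.2.1).
4. The categories include no level for unobserved time (6.3.2).
5. The missing-value count in 6.7.1 works only if something marks the value as missing. No text says that a short look-back does so.

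Followed as written, a patient with a short history and no recorded event falls in the category for no relapses.

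**Direction.** Unobserved time can hide relapses but cannot add any. This gap therefore moves patients towards fewer relapses only.

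**Illustrative size.** Assumptions, none of them from the protocol:

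- relapses follow a Poisson process with rate r = 0.5 or 1.0 per year;
- a share s = 10% or 25% of patients have only h = 0.5 years observed, and the rest have the full 2 years;
- r is the same in both groups, and recording is complete while a patient is observed.

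Formulas for the 2-year window:

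- true probability of no relapse = exp(−2r)
- recorded probability with h years observed = exp(−rh)
- overstatement in the cohort = s × [exp(−rh) − exp(−2r)]

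| r per year | True, no relapse | Recorded, 6 months observed | Difference | Cohort excess, s = 10% | Cohort excess, s = 25% |
|---|---|---|---|---|---|
| 0.5 | exp(−1) = 36.8% | exp(−0.25) = 77.9% | 41.1 points | 4.1 points | 10.3 points |
| 1.0 | exp(−2) = 13.5% | exp(−0.5) = 60.7% | 47.1 points | 4.7 points | 11.8 points |

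With 12 of the 24 months observed, the recorded shares are 60.7% (r = 0.5) and 36.8% (r = 1.0), still well above 36.8% and 13.5%.

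Among the short-history patients the top category empties. The recorded share with two or more relapses is 2.6% against a true 26.4% at r = 0.5, and 9.0% against 59.4% at r = 1.0.

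For the 1-year window with 6 months observed, the difference is exp(−0.5r) − exp(−r). At r = 0.5 that is 77.9% − 60.7% = 17.2 points; at r = 1.0 it is 60.7% − 36.8% = 23.9 points. The cohort excess is about 2 points at s = 10% and 4 to 6 points at s = 25%.

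**The case against.** **Long data histories.** The sources reach back far: 10 years in SNDS, January 2008 in the German claims data, a mean of 10 years in SIDIAP, an average of twelve years in PHARMO, and a cohort running since 2010 in NOMADMUS (6.4). Most patients will probably have two observed years. This stands as a limit on size, but these figures describe a source or an average, not a condition on each patient. Entry is individual: birth or immigration in SNDS, assignment to a covered centre in SIDIAP, accrual in RISM. RISM's NMOSD module dates from July 2022, and the Italian study period starts in May 2023 (Table 1). RISM makes onset date and relapses mandatory and held NMOSD data before the module, so it may record earlier relapses retrospectively. The protocol does not say whether it does.

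**The SAP and the missing-value rule.** Section 6.3.2 defers the relapse definition to the SAP, and 6.7.1 provides for missing values and for summarising only available data. The SAP could therefore set short histories to missing. But what is deferred is how a relapse is identified. The windows and categories are stated outright, and nothing says that short look-back counts as missing.

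**A stronger reading to avoid.** A reader might infer that the treatment and admission proxies count the first attack of the disease as a relapse, so that the variable errs upwards as well. The protocol does not support this. It neither counts nor excludes the first attack, its proxies are examples, the diagnoses are still to be selected, and the definition is left to the SAP and the registries. Table 4 cannot size such an effect either. Pairing its low incidence with its low prevalence, and high with high, gives 2 × 0.05/0.52 = 19% and 2 × 0.40/4.4 = 18% of prevalent patients within two years of onset. Other pairings of the same ranges give 2 × 0.05/4.4 = 2% or 2 × 0.40/0.52, which exceeds 100%.

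**Conclusion.** The point holds for unobserved look-back and for that alone. The protocol reports relapse counts over fixed windows for all new users without requiring the windows to be observed and without a category for those that were not. The resulting error runs in one direction, towards too few relapses, and can differ between sources.

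The size of about 4 to 12 percentage points in the 2-year share with no relapse rests wholly on the assumed relapse rate and the assumed share with six months of history. With fewer short-history patients it shrinks in proportion; with none it vanishes.

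The consequence is modest. Relapse history is one descriptive variable under objective 1. It enters no eligibility rule, and neither planned subgroup (concomitant immunosuppressants, age over 65) is defined by it. The change is still worth making because the bias is avoidable at almost no cost.

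**What to change.** In section 6.3.2, and in the SAP derivation that follows from it:

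- Derive the 1-year classification only in patients with at least 12 months of observed time before index, and the 2-year classification only in those with at least 24 months. Accept registry-documented relapse history that covers the window as equivalent.
- Report all other patients in a separate level, such as 'insufficient history', with number and percentage by data source.

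This needs wording and one derived variable for observed pre-index time. No patient leaves the cohort and no other analysis changes. The cost is a smaller denominator for this one characteristic, most noticeably in sources where patients enter close to treatment start.
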